### **21.11.2 OSDI QUESTIONNAIRE**

The OSDI has 12 questions. Based on the answers provided by the subject, study staff calculate the overall OSDI Total score (from 0-100) and scores for the three subscales according to the OSDI instructions. Based on the recommended cutoffs for OSDI Total score, the severity of the subject's dry eye symptoms will be categorized as follows:

- Normal – 0-12
- Mild – 13-22
- Moderate – 23-32
- Severe – 33 or higher

### **21.11.3 SANDE QUESTIONNAIRE AND EYE DRYNESS VAS**

The SANDE is a simple dry eye instrument containing two items measuring the frequency and severity of symptoms, each is assessed on a 100 mm visual analog scale (VAS) ranging from 'Never/Very comfortable' to 'All the time/Very severe' and scored from 0 to 100. The Eye Dryness Visual Analog Scale measures subject's level of discomfort related to eye dryness ranging from "No discomfort/maximal discomfort."

Three scores will be obtained from the SANDE:

- Frequency score (ranging from 0 to 100): The distance (in mm) between the left end of the scale and the subject's response.

- Severity score (ranging from 0 to 100): The distance (in mm) between the left end of the scale and the subject's response.
- A SANDE Total score (also ranging from 0 to 100): This is calculated as the square-root of the product of the Frequency and Severity scores.

The Eye Dryness Score is derived from the Eye Dryness Visual Analog Scale. The Eye Dryness Score (ranging from 0 to 100) is the distance (in mm) between the left end of the scale and the subject's response.

Study staff should instruct subjects to record their response to each question by placing a vertical line (not an "X") across the horizontal line of the visual analog scale.

#### **21.11.4 TREATMENT PREFERENCE QUESTIONNAIRE (RESTASIS GROUP ONLY)**

Treatment Preference Questionnaire will be administered in subjects randomized to Restasis group at their post TearCare 12M visit. Questionnaire completion guidelines described in Section 21.11.1 should be followed to administer this questionnaire.

## 22 APPENDIX B – STATISTICAL ANALYSIS PLAN

### 22.1 ANALYSIS POPULATIONS

- Intent-to-Treat Population - The intent-to-treat (ITT) population includes all randomized subjects. The primary and secondary efficacy analyses will be performed on the ITT population. Subjects will be analyzed as randomized.
- Due to the inclusion criteria revision in May of 2021 for Schirmer's test parameters, the modified ITT (mITT) population includes all ITT except for those subjects that did not meet the revised eligibility at the baseline visit.
- Per Protocol Population – The per protocol (PP) population (subset of mITT) includes all subjects who have at least one follow-up visit and have no major protocol deviations, including specifically no use of dry-eye medications (Doxycycline, Xiidra). Subjects will be analyzed as treated. The primary and secondary efficacy analyses will be performed on the per protocol population.
- Safety Population – The safety population will include all subjects on whom the TearCare or Restasis is attempted. The safety population will be analyzed for all safety assessments. Subjects will be analyzed as treated.

### 22.2 STATISTICAL HYPOTHESES

The primary study hypotheses regard the superiority of the TearCare procedure as compared to Restasis, for Tear Break-Up Time (TBUT) and total OSDI. The primary endpoints will be tested for TearCare in a hierarchical fixed sequence. The statistical hypotheses are stated in terms of one-sided hypotheses, although statistical testing will be two-sided.

To demonstrate superiority of the TearCare procedure to the Restasis control for TBUT we will test the following hypotheses:

$H_{01}$ : There is no difference between TearCare and Restasis in the mean change from baseline in TBUT at 6 Months.

$H_{11}$ : The mean change from baseline in TBUT at 6 Months is greater with TearCare than with Restasis.

If  $H_{01}$  is rejected, then the study will be considered a success and we will test the following hypotheses to further demonstrate superiority of the TearCare procedure to the Restasis control for total OSDI:

$H_{02}$ : There is no difference between TearCare and Restasis in the mean change from baseline in total OSDI at 6 Months.

H12: The mean change from baseline in total OSDI at 6 Months is less with TearCare than with Restasis.

## 22.3 MULTIPLICITY CONSIDERATIONS

To address the multiple endpoints in this study, the primary and secondary effectiveness endpoints have been ordered in a hierarchical structure. Using this fixed sequence testing strategy, the family-wise Type I error rate will be maintained at the 0.05 significance level for testing the two primary effectiveness endpoints and the secondary effectiveness endpoints.

## 22.4 SAMPLE SIZE CALCULATIONS

### 22.4.1 TEAR BREAKUP TIME

A minimum of 310 subjects, approximately 155 in the TearCare group and 155 in the Restasis group, will be enrolled and randomized in the study. With an estimated 10% drop out rate at 6 months, a minimum of 139 subjects in each group are expected to be available for the primary efficacy analysis. Assuming a common standard deviation of 2 seconds for the change from baseline in TBUT at 6 months, a sample size of 139 subjects per group will have 98% power to detect a mean difference of 1 second between TearCare and Restasis at a two-sided significance level of 0.05. Assuming an overall 15% drop out rate, a minimum of 100 subjects are expected to be available at 24 months in each group to achieve 90% statistical power. This calculation is conservatively based upon prior TearCare clinical trial data, published data on Restasis, and the use of a two-sample t-test.

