Study Duration for Each Subject	Up to 24 months
Total Study Duration	Approximately 40 to 50 months
Schedule of Visits	
TearCare group (Study Device):
 
Baseline, Procedure Day 0, Day 1, Week 1, Month 1, Month 3, Month 5, Month 6, Month 9, Month 12, Month 15, Month 18, Month 24
 
TearCare procedure will be given within 7 days of Baseline and at 5 Months. Beginning at 9 Months, subjects will receive an additional TearCare procedure when TBUT drops lower than Baseline or within 2 seconds of baseline AND if OSDI worsens by at least 15 points compared to the previous visit*.
 
(*Based on the recommended cutoffs for OSDI Total score, the severity of the subject's dry eye symptoms is categorized as; Normal – 0-1, Mild – 13-22, Moderate – 23-32, Severe – 33 or higher)
 
Restasis group (Control):
 
Baseline, Restasis Day 0, Day 1, Week 1, Month 1, Month 3, Month 6
 
Subjects will be required to self-administer 1 drop twice a day from baseline through the Month 6 visit. At Month 6, subjects from the Restasis group will be crossed over to the TearCare group and will receive one (1) TearCare procedure and will be followed as below:
 
Day 1, Week 1, Month 1, Month 9, Month 12

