### 7.1 STUDY DEVICE AND CONTROL GROUP

In this study, TearCare procedures using the TearCare System (study device) will be compared with Restasis (control group).

TearCare procedures in this study will include an in-office eyelid debridement, 15-minute bilateral thermal session with the TearCare System, immediately followed by manual expression of the meibomian glands using the Clearance Assistant Plus device. Subjects randomized to TearCare will receive one in-office TearCare procedure within 7 days of the Baseline visit and at 5 Months. Beginning at 9 Months, subjects will receive an additional TearCare procedure when TBUT drops lower than Baseline or within 2 seconds of baseline AND if OSDI worsens by at least 15 points compared to the previous visit.

Subjects randomized to Restasis group will be required to self-administer 1 drop twice a day from baseline through the Month 6 visit. At Month 6, subjects will be crossed over to the TearCare group and will receive one (1) TearCare procedure.

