## 9.2 TABLE 4: RESTASIS STUDY VISIT SCHEDULE

Restasis								Restasis CROSSOVER to TearCare					
Visit	Baseline	Day 0	Day 1	Wk 1	1 M	3 M	6 M/TearCare	Post Procedure			9 M	12 M	
Window days	-7 to 0	0	1	5-9	21-35	70-90	150-180	Day 1	Wk 1	1 M	220-280	320-390	
								1	5-9	21-35			
Informed Consent a	X												
Demographics, Ocular & Medical Hx	X												
Medication use	X			X	X	X	X		X	X	X	X	
Questionnaires (OSDI, SANDE, Eye Dryness Score)	X			X	X	X	X		X	X	X	X	
BCVA b	X		X c	X c	X	X	X	X c	X c	X	X	X	
Blink rate	X			X			X		X			X	
Slit Lamp Exam	X		X	X	X	X	X	X	X	X	X	X	
TBUT	X			X	X	X	X		X	X	X	X	
Corneal Staining	X			X	X	X	X		X	X	X	X	
Conjunctival Staining	X			X	X	X	X		X	X	X	X	
Schirmer Test	X			X	X		X		X	X		X	
MGSS	X			X	X	X	X		X	X	X	X	
IOP d	X		X	X	X	X	X	X	X	X	X	X	
Subject Eligibility	X												
Randomization	X												
Restasis (1gtt BID)		X	X	X	X	X							
AE Assessment	X	X	X	X	X	X	X	X	X	X	X	X	
Crossover and TearCare Procedure							X						
Treatment preference questionnaire												X	
Eye Lubricant/Drop Log					X	X	X		X	X	X	X	

a Subjects may sign the informed consent up to 60 days in advance of the baseline visit.

b Restasis must be dispensed within 7 calendar days of the Baseline visit. If scheduling permits, it may be dispensed on the same day as the Baseline visit following Randomization.

c BCVA should be collected after manifest refraction using ETDRS visual acuity chart

d On Day 1 and Week 1, Best Corrected Spectacle Visual Acuity (BCSVA using ETDRS) is measured without manifest refraction (MR). If the VA has worsened by  $\geq 10$  letters (per ETDRS) from baseline, then MR should be performed, the ETDRS measurement should be repeated, and the VA post-MR should be recorded.

e IOP measured via applanation tonometry should be measured at baseline using standard of practice at each site with the same method to be used for all consecutive visits in the study.

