## 12.5 EFFECTIVENESS ENDPOINTS AND ANALYSIS METHODS

All primary and secondary endpoints will be evaluated at 6 months. Outcomes measured on a per-eye basis will be analyzed using data from both eyes, with linear mixed effect models to account for within-person correlation (correlation between right and left eyes) as described in Appendix B.

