## **12.7 SAMPLE SIZE CALCULATION**

A sample size of 200 subjects is estimated to provide sufficient power (90%) for this study. Nonetheless, given the 24 months follow up period and in an attempt to collect additional data regarding changes in the signs and symptoms of dry eye disease, up to 300 subjects, approximately 150 in the TearCare group and 150 in the Restasis group, will be enrolled and randomized in the study. This will provide more than 90% power to meet the TBUT effectiveness endpoint and sufficient precision around the adverse event estimates. The sample size also takes into account an estimated 10% dropout rate per 6 months. Details of the sample size calculation can be found in Appendix B.

In May of 2021, the study protocol was revised to update the appropriate Schirmer test parameters for inclusion. Since the study treated some subjects that did not meet these parameters at baseline, the planned sample size of the study was increased to approximately 310 subjects, approximately 155 in the TearCare group and 155 in the Restasis group.

In August of 2022, the sample size was increased to 350 subjects, with up to 175 in the TearCare group and up to 175 in the Restasis group in order to account for additional subjects (an estimated 10) not meeting all eligibility criteria and a possible slightly higher dropout rate per 6 months (~11%).

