### 22.4.2 SAFETY

With an estimated 10% drop out rate per 6 months, a minimum of 98 subjects are expected to be available for analysis at 24 months in the TearCare group. For an AE that occurs at a rate of 5% within the TearCare group, this sample size would yield a 95% confidence interval with a margin of error of 4.4%; for an AE that occurs at rate 10%, the margin of error would be 6.0% and for an AE that occurs at rate 20%, the margin of error would be 8.1%.

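### SAP 22.4.1 states 90% power for two groups at 24 months, but no Restasis comparison exists then, and its 15% overall dropout conflicts with the 10% per 6 months used elsewhere

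*Combined protocol and SAP*

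**What the plan says.** Section 22.4.1 starts from a minimum of 155 randomised per group. "With an estimated 10% drop out rate at 6 months, a minimum of 139 subjects in each group are expected to be available", and 139 per group is said to give 98% power for a 1-second difference in TBUT change with an SD of 2 seconds, two-sided 0.05, by two-sample t-test. The paragraph then moves to an overall dropout of 15% and says "a minimum of 100 subjects are expected to be available at 24 months in each group to achieve 90% statistical power".

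The rest of the plan sets the comparison and the follow-up as follows:

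- Section 12.5: "All primary and secondary endpoints will be evaluated at 6 months". The hypotheses in 12.5.3 and 22.2 are also for Month 6 only.
- Section 7.1, for the Restasis group: "At Month 6, subjects will be crossed over to the TearCare group and will receive one (1) TearCare procedure".
- Table 4 (section 9.2) heads the later visits "Restasis CROSSOVER to TearCare". The synopsis lists those visits as "Day 1, Week 1, Month 1, Month 9, Month 12". Only Table 3, the TearCare schedule, has a Month 24 column.
- Section 9.3 says, to the contrary, that all subjects are followed for up to 24 months.

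On dropout, section 12.7 says "The sample size also takes into account an estimated 10% dropout rate per 6 months", and its August 2022 paragraph allows for about 11% per 6 months. Section 22.4.2, for the TearCare group, says "With an estimated 10% drop out rate per 6 months, a minimum of 98 subjects are expected to be available for analysis at 24 months".

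**The concern.** The 24-month sentence follows directly on the TearCare-versus-Restasis power statement and refers to each group, so it reads as power for that same contrast at Month 24. By then the plan has no Restasis arm, and it gives no Month 24 hypothesis, SD or effect size. The sentence also takes its count from a dropout rate that differs from the one in the next subsection and in the protocol body.

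What is at stake is how the 24-month results are described. Section 12.7 gives the 24-month follow-up as a reason for enrolling beyond the 200 subjects needed for 90% power, and sends the reader to Appendix B for the details. A reader could then cite the SAP as having prespecified a powered controlled comparison at 24 months, when the Month 24 data will come from the randomised TearCare arm alone.

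**Working it through.** **Inputs.** From 22.4.1: 155 per group, difference 1 second, SD 2 seconds (given for Month 6 change only), two-sided 0.05, t-test, 10% lost by Month 6, 15% overall. From 12.7 and 22.4.2: 10% per 6 months. From the August 2022 paragraph of 12.7: up to 175 per group and about 11% per 6 months.

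**1. Month 6 figure.** Retained: 155 × 0.90 = 139.5, so 139. Noncentrality = 1 / (2 × √(2/139)) = 4.17. Power is 98.6%, by both the normal approximation and the noncentral t. The stated 98% reproduces.

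**2. The 90% attached to 100 per group.** With the same difference and SD, noncentrality = 1 / (2 × √(2/100)) = 3.54. Power is 94.2% (normal) or 94.0% (t). For 90%, 85 per group (normal) or 86 (t) are enough. So 90% holds as a floor; it is not the power that 100 per group gives. The calculation also borrows the Month 6 SD and effect, because none is given for Month 24.

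**3. Who is there at Month 24.**

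| | Randomised TearCare | Randomised Restasis |
|---|---|---|
| Treatment after Month 6 | TearCare | crossed over to TearCare |
| Last scheduled visit | Month 24 | Month 12 |
| Scheduled at Month 24 | yes | none |

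There is no TearCare-versus-Restasis contrast at Month 24 for a power to describe.

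**4. Dropout bases, from 155 randomised.**

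- 15% overall: 155 × 0.85 = 131.75, so 131.
- 10% per 6 months over four periods: 155 × 0.9⁴ = 101.7, so 101 (34% loss).
- A count of 100 means 1 − 100/155 = 35.5% loss.
- Taking the 15% as a further loss from the 139 at Month 6: 139 × 0.85 = 118.

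The 100 in the sentence is close to the 10%-per-6-months result. It does not follow from the 15% that the sentence cites.

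**5. Loss implied between Months 6 and 24.** If 10% are lost by Month 6 and 15% overall, the further loss is 1 − 0.85/0.90 = 5.6%. At 10% per 6 months it is 1 − 0.9³ = 27.1%.

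**6. The 98 in 22.4.2.** 150 × 0.9⁴ = 98.4, while 155 × 0.9⁴ = 101.7. The 98 therefore fits the 150 per group in the first paragraph of 12.7, not the current 155.

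**7. At the later assumptions in 12.7.** At 11% per 6 months, 155 × 0.89⁴ = 97.3 and 175 × 0.89⁴ = 109.8.

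**The case against.** There are four points on the other side.

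- **Floors.** The sentence gives a minimum. Since 131 exceeds 100, and 100 per group gives more than 90%, neither number is false as a lower bound. This stands. It does not supply the missing comparison or make the two dropout rates agree.
- **Other sections prevent the misreading.** Sections 12.5 and 22.2 fix the tests at Month 6, and 22.4.3 ties power to the primary TBUT analysis and links 24 months only to the precision of adverse event estimates. This limits the harm, and no test, alpha or success rule uses the sentence. It does not make the sentence correct.
- **Possible leftover.** With 200 subjects, 100 per group less 15% is 85 per group, which gives 90.0% by t-test. The sentence may be what remains of that calculation. This is inference only. If it is right, the 5.6% in step 5 was never a real planning assumption, but the sentence is still misplaced as it stands.
- **Follow-up to 24 months in 9.3.** This conflicts with Table 4. Even if it governed, the controls would have had TearCare from Month 6, so no Restasis contrast would return. The 12-month post-TearCare visit in 21.11.4, read as generously as possible, reaches only about Month 18.

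The adverse event margins in 22.4.2 are not in question. A t-based interval with an n − 1 variance at n = 98 gives 4.39, 6.05 and 8.06 points before rounding, consistent with the stated 4.4, 6.0 and 8.1.

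**Conclusion.** The concern holds. Section 22.4.1 states a two-group power at 24 months that the design cannot have, with 0 Restasis subjects scheduled at Month 24 against at least 100 stated. Its 15% overall dropout is incompatible with 10% per 6 months: 131 against 101 remaining of 155.

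The effect is limited. Month 6 power (98.6% with 139 per group), the tests and the success rule are unchanged. This is a correction to the SAP's sample size text and no threat to the primary analysis.

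The conclusion rests on Table 4 and the synopsis being the operative Restasis schedule, and on dropout compounding over four 6-month periods. If the loss were linear at 10% of those randomised per period, 155 × 0.6 = 93 would remain, which is further still from 131.

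**What to change.** 1. Delete the 24-month power sentence from 22.4.1. Alternatively, replace it with a statement that the randomised TearCare-versus-Restasis comparison ends at Month 6, and that Month 24 data come from the randomised TearCare arm alone and are reported with 95% confidence intervals. Deletion is enough; the replacement adds a reporting commitment.
2. Use one dropout assumption in 12.7, 22.4.1 and 22.4.2, and give the Month 24 TearCare count that follows from it. From the 155 minimum this is 101 at 10% per 6 months, 97 at 11%, or 131 if 15% overall is really meant. If the ceiling of 175 is reached at 11%, it is about 110. Update the 98 in 22.4.2 to match.
3. Reconcile the follow-up statement in 9.3 with Table 4, and the SAP minimum of 310 with the 350 in 9.3 and 12.7.

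The cost is wording in the SAP and in the matching protocol sections. Design, tests, alpha and Month 6 power do not change.

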### 22.4.2 SAFETY

With an estimated 10% drop out rate per 6 months, a minimum of 98 subjects are expected to be available for analysis at 24 months in the TearCare group. For an AE that occurs at a rate of 5% within the TearCare group, this sample size would yield a 95% confidence interval with a margin of error of 4.4%; for an AE that occurs at rate 10%, the margin of error would be 6.0% and for an AE that occurs at rate 20%, the margin of error would be 8.1%.

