Device related ocular adverse events were reported in two subjects (loss of visual acuity) for the TearCare® group and three subjects (loss of visual acuity, corneal abrasion and foreign body sensation) for the LipiFlow® group.

Figure 5: TBUT, MGSS, Corneal and Conjunctival staining per follow up time point. Blue legends, line and bars represent TearCare group and red legends, line and bars represent LipiFlow group.

[figure not shown]
[figure not shown]

Figure 6: SANDE, EDS and OSDI scores per follow up time point Blue legends, line and bars represent TearCare group and red legends, line and bars represent LipiFlow group.

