### 22.4.3 SAMPLE SIZE SUMMARY

With a minimum of 155 in the TearCare group and 155 in the Restasis group, the power for the primary efficacy analysis of TBUT exceeds 90% and provides sufficient precision around the adverse event estimates through 24 months.

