## **22.6 SAFETY ANALYSIS**

All adverse events will be reported by treatment group and AE category. Any serious adverse events will be completely described in the study report. The primary safety endpoint will be summarized for each treatment group.

We will compute the incidence of ocular events in two ways: first as a simple proportion, counting the number of subjects with any event (that is, counting the first event per person in either eye), then as an incidence rate, counting all events including repeated events per subject.

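### The adverse-event precision in SAP 22.4.2 was not updated with the sample size, its symmetric margins understate the upper limit at low event rates, and 22.6 plans no interval for the primary safety endpoint

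*Combined protocol and SAP*

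**What the plan says.** SAP 22.4.2 concerns the TearCare arm and begins: "With an estimated 10% drop out rate per 6 months, a minimum of 98 subjects are expected to be available for analysis at 24 months". On the precision that this number buys, it says: "For an AE that occurs at a rate of 5% within the TearCare group, this sample size would yield a 95% confidence interval". The half-width given there is 4.4 percentage points, and those given for event rates of 10% and 20% are 6.0 and 8.1 points. The section states neither the starting number per group nor the interval formula.

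SAP 22.4.3 concludes that a minimum of 155 per group "provides sufficient precision around the adverse event estimates through 24 months". Protocol 12.7 makes a similar claim. It also records the history of the group size: 150, then about 155 (May 2021), then up to 175 with dropout of about 11% per 6 months (August 2022). SAP 22.4.1 uses 155 per group and expects at least 100 per group at 24 months.

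On analysis, SAP 22.6 says: "The primary safety endpoint will be summarized for each treatment group". Sections 12.6.4 and 22.6 add a proportion of subjects with any ocular event and an incidence rate counting repeat events. Neither names a confidence interval or a comparison between groups. The safety population is everyone on whom treatment is attempted (12.2, 22.1). The synopsis states the primary objective as safety and effectiveness compared with Restasis.

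**The concern.** The only calculation behind the claim of sufficient safety precision appears to rest on a group size that the plan has twice replaced. It also describes precision by one symmetric half-width. At a 5% rate and n = 98 about five events are expected, and the binomial distribution is then clearly skewed. A symmetric interval puts too little of its width above the estimate, which is the side that matters for safety. A reader would take the true rate to be bounded more tightly from above than the data could show.

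The analysis section does not make up for this. As written, the primary safety endpoint could be reported as two proportions with no measure of uncertainty and no estimated difference, although the objective is comparative.

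**Working it through.** **Inputs.** 22.4.2: n = 98, 10% dropout per 6 months (four periods to 24 months), margins 4.4, 6.0 and 8.1. 12.7: 150, 155 and up to 175 per group, with about 11% dropout for the last. 22.4.1 and 22.4.3: 155 per group.

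**1. Where 98 comes from.** Expected number at 24 months = N × (1 − d)^4.

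| N per group | d per 6 months | Expected at 24 months |
|---|---|---|
| 150 | 10% | 98.4, so 98 |
| 155 | 10% | 101.7, so 101 |
| 175 | 11% | 109.8, so 109 |

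Only the first row gives 98. This is an inference, since 22.4.2 states no starting N.

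**2. Reproducing the margins at n = 98.**
- Normal formula, 1.96 × √(p(1 − p)/98): 4.3, 5.9 and 7.9 points.
- t multiplier (97 df, 1.985) with an n − 1 divisor, 1.985 × √(p(1 − p)/97): 4.39, 6.05 (6.046 before rounding) and 8.06 points. These round to the stated 4.4, 6.0 and 8.1.

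The plan's figures are therefore reproduced.

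**3. Coverage of a symmetric interval at a true rate of 5%.** For each count x from 0 to n, form the interval around x/n. Then add the Binomial(n, 0.05) probabilities of the counts whose interval contains 5%.

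| n | Coverage | Upper limit too low | Lower limit too high |
|---|---|---|---|
| 98 | 87.0% | 12.7% | 0.4% |
| 109 | 90.6% | 8.6% | 0.8% |

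The normal and t forms give the same coverage at these two sizes. At n = 98 the upper limit is too low whenever two or fewer events are seen. Wilson and exact intervals both cover 96.9% at n = 98.

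**4. Exact (Clopper-Pearson) limits.** The lower limit is the 2.5% quantile of Beta(x, n − x + 1). The upper limit is the 97.5% quantile of Beta(x + 1, n − x).
- 5 of 98 (5.1%): 1.7% to 11.5%, that is +6.4 and −3.4 points, against the stated ±4.4.
- 5, 11 and 22 of 109: 1.5% to 10.4%, 5.1% to 17.3%, and 13.1% to 28.9%.

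**The case against.** Much of the opposing case stands.

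- **A reader might infer that the margins are miscalculated**, because the usual normal formula gives 4.3, 5.9 and 7.9. The documents do not support that. A standard t-based form gives the stated values, no formula is named, and the stated margins are the wider ones by at most 0.2 points.
- **The outdated count is conservative.** 98 is given as a minimum, and both 101 and 109 satisfy it. At n = 109 the normal margins are 4.1, 5.6 and 7.5 points, all narrower than stated. Only a mix that the plan does not make (155 with 11% dropout, 155 × 0.89^4 = 97.3) falls just below it.
- **A reader might infer that the trial's adverse-event analysis will have 87% coverage.** It will not necessarily, because no interval is prespecified. The figure describes the kind of interval that the planning margin implies. It also moves erratically with n: for the normal form it is 94.5% at n = 94 and 85.2% at n = 95. Read only as a distance around a known 5% rate, ±4.4 points captures the observed proportion 96.9% of the time at n = 98.
- **The denominator differs.** The any-event proportion uses all treated subjects, near 155 to 175, and not 24-month completers. At those sizes coverage of the normal interval at 5% is 94.3% and 93.4%, with margins of 3.4 and 3.2 points.
- **The earlier randomized trial is weak evidence that the planning rates start too high.** Section 5.2.4 says: "Device related ocular adverse events were reported in two subjects (loss of visual acuity) for the TearCare® group". If 136 randomized 1:1 means about 68 per arm, that is about 3%. But it follows a single treatment, and the exact interval for 2 of 68 is 0.4% to 10.2%, which includes 5% and 10%.

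These points do not remove the mismatch of group sizes within the plan, the asymmetry at low rates, or the missing interval in 22.6.

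**Conclusion.** The point holds as a consistency and reporting matter of low to moderate severity. Section 22.4.2 was very probably left at 150 per group while the rest of the plan moved to 155 and then up to 175. Updating the count alone would make the precision look slightly better.

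The substantive weakness is the symmetric margin. At about five events the exact upper limit lies 6.4 points above the estimate at n = 98, where the plan states 4.4. An interval of the implied kind falls short of 95% coverage by 8.0 points at n = 98 and by 4.4 at n = 109, almost entirely on the upper side. These figures assume a true rate of 5% and a symmetric normal or t interval. The 109 further assumes that the full 175 are randomized and that dropout is 11% in each 6-month period.

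The more useful change concerns 22.6, where the primary safety endpoint has no stated uncertainty and no between-group estimate. The documents state no safety hypothesis, so estimation is what is missing and not a test. Nothing here affects the primary effectiveness analysis.

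**What to change.** **22.4.2.** State the starting number and dropout rate, and bring them into line with 12.7, 22.4.1 and 22.4.3. Name the interval method (exact or Wilson) and replace the symmetric margins with limits. For n = 109 use the exact limits in step 4 of the working. Say that these describe subjects still followed at 24 months, whereas the any-event proportion in 22.6 uses all treated subjects.

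**22.6 (and 12.6.4).** Report the primary safety endpoint in the safety population with exact 95% limits for each arm. Add the TearCare minus Restasis risk difference with a 95% confidence interval for Day 0 to Month 6, counting events before the crossover procedure, as estimation without a hypothesis test. Tables 3 and 4 give different Month 6 windows (170–210 and 150–180 days), so the cut-off needs to be defined.

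**Cost.** Some SAP wording and one extra table, with no new data and no change to the sample size. The stated upper limit becomes less favourable.
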